7.5.1.1 Summaries of Primary Efficacy Endpoint Within Subgroups

The primary efficacy endpoint will be summarized within the following subgroups using the mITT and the observed values approach:

- Baseline viral load: < 100,000c/mL, ≥ 100,000c/mL
- Baseline CD4 category: < 100cells/mm³, 100 to < 200cells/mm³, 200 to < 350cells/mm³, 350 to < 500cells/mm³, ≥ 500cells/mm³
- Gender

- Race
- HIV-1 clade

7.5.2 Secondary Efficacy Endpoints

7.5.2.1 Proportion of Subjects with Plasma HIV-1 RNA < 40c/mL at Weeks 48 and 96

The proportion of subjects with HIV1 RNA < 40c/mL at Weeks 48 and 96 will be assessed analogously to the primary efficacy endpoint using the snapshot algorithm. Summaries within subgroups identified for the primary analysis will be provided for Week 48 and 96 using the mITT and the observed values approach. Also a time to loss of virologic response analysis will be done.

7.5.2.2 Proportion of Subjects with Plasma HIV-1 RNA < 200c/mL at the Week 24, 48 and 96 Snapshot

The proportion of subjects with plasma HIV-1 RNA < 200c/mL at Week 24, 48 and 96 will be summarized using mITT and the observed values approach, analogously to the primary efficacy endpoint using the snapshot algorithm. No summaries within subgroups will be provided.

7.5.2.3 Change from Baseline in Plasma HIV-1 RNA (\log_{10}) over Time

The change from baseline in plasma HIV-1 RNA (\log_{10}) will be summarized over time for the treated subjects using observed values. The mean changes from baseline will be plotted at each scheduled visit (except Week 2) through Week 96 by treatment arm, with error bars representing 1 standard error. The change from baseline in plasma HIV-1 RNA (\log_{10}) at Week 24, 48 and 96 will be presented graphically using box plots. The change from baseline will also be provided for the subgroups identified for the primary analysis.

7.5.2.4 Changes from Baseline in CD4+ and CD8+ T-cell Count over Time

CD4+ and CD8+ T-cell counts and changes from baseline will be summarized at each scheduled visit through Week 96 by treatment arm using observed values. The mean changes from baseline will be plotted at each scheduled visit through Week 96 by treatment arm, with error bars representing 1 standard error. The change from baseline in CD4+ and CD8/ T-cell counts at Week 24, 48 and 96 will be presented graphically using box plots. Also the percentage of CD4+ T-cells and changes from baseline will be summarized at each scheduled visit through Week 96. The change from baseline will also be provided for the subgroups identified for the primary analysis.

7.5.2.5 Newly-emergent Genotypic Substitutions, IC₅₀ Fold Changes from Baseline and Newly-emergent Gag Polymorphisms

Viral resistance is measured using the “PhenoSense GT plus Integrase” assay from Monogram (LabCorp). The PhenoSense GT plus Integrase is used to determine both genotypic and phenotypic resistance to Nucleoside Reverse Transcriptase Inhibitors (NRTIs), Non-Nucleoside Reverse Transcriptase Inhibitors (NNRTIs), Integrase Inhibitors (INIs), and Protease Inhibitors (PIs). The “PhenoSense Gag” assay is used for determining phenotypic susceptibility to BMS-955176. HIV-1 Gag sequencing data will be obtained from the NGS-Gag Quantitative Sequencing (QS) assay.

Genotypic substitutions and phenotypic resistance profiles focus on subjects with on-treatment isolates.

Newly emergent phenotypic resistance to a drug is defined as a baseline fold change \leq the cut-off for reduced susceptibility and an on-treatment fold change $>$ the cut-off for reduced susceptibility. The newly emergent phenotypic resistance profile (using all on-treatment isolates) will be tabulated by treatment arm for treated subjects with on-treatment resistance testing done.

Newly emergent phenotypic resistance to BMS-955176 is defined as a baseline fold change IC₅₀ ≤ 3 and an on-treatment fold change IC₅₀ > 3 . The newly emergent phenotypic resistance to BMS-955176 (using all on-treatment isolates) will be tabulated by treatment arm for treated subjects with on-treatment resistance testing done.

Newly emergent genotypic substitutions (using all on-treatment isolates) are tabulated by treatment arm for treated subjects with on-treatment resistance testing done. The presentation will be similar to the one for baseline genotypic substitutions.

The maximum change from baseline in BMS-955176 IC₅₀ and the maximum BMS-955176 fold change IC₅₀ (FC-IC₅₀) through Week 96 will be summarized for all treated subjects with on-treatment phenotypic resistance profile. In addition, the proportion of subjects with a > 3 fold increase from baseline in BMS-955176 FC-IC₅₀ (i.e., BMS-955176 FC-IC₅₀ on-treatment divided by BMS-955176 FC-IC₅₀ at baseline > 3) will be summarized. The Gag polymorphisms will be summarized for subjects with a > 3 fold increase from baseline in BMS-955176 FC-IC₅₀. These summaries will use all of the data present in the database at the time of lock.

Newly emergent Gag polymorphisms at the selected positions will be summarized by treatment arm for treated subjects with on-treatment resistance testing done, overall and by baseline HIV subtype. In addition, any newly emergent Gag deviation will be summarized for treated subjects with on-treatment resistance testing done, overall and by baseline HIV subtype.

All summaries described in this section will also be provided for treated subjects that are identified as protocol defined virologic failures.

Protocol Defined Virologic Failure (PDVF) is defined by a subject meeting one of the following criteria (see Protocol, Section 5.4.1.2):

- Confirmed $> 1 \log_{10}$ c/mL increase in HIV-1 RNA at any time above nadir level where nadir is ≥ 40 c/mL
- Confirmed HIV-1 RNA ≥ 400 c/mL after Week 24
- Confirmed HIV-1 RNA ≥ 40 c/mL if prior suppression to < 40 c/mL
- Failure to have the last on-treatment HIV-1 RNA to < 400 c/mL within Week 24, 48, or 96 week snapshot window
- Failure to achieve $> 1 \log_{10}$ c/mL decrease in HIV-1 RNA by Week 8

7.5.3 Exploratory Efficacy Endpoints

7.5.3.1 Proportion of Subjects with Plasma HIV-1 RNA within Certain Range over Time

The proportion of subjects with HIV-1 RNA:

- < 40 c/mL
- 40 to < 100 c/mL
- 100 to < 200 c/mL
- 200 to < 400 c/mL
- > 400 c/mL

will be presented by visit using the observed values approach.

7.5.3.2 Efficacy Summaries by Baseline Gag Polymorphisms

To assess the impact of baseline gag polymorphisms the following efficacy endpoints will be summarized by all combinations of baseline gag polymorphisms at selected positions:

- Proportion of subjects with plasma HIV-1 RNA < 40 c/mL at Weeks 24, 48 and 96
- Proportion of subjects with plasma HIV-1 RNA < 200 c/mL at Weeks 24, 48 and 96
- Change from baseline in \log_{10} HIV-1 RNA at Weeks 4, 8, 12, 24, 48 and 96

7.5.4 Futility Analysis

An analysis of virologic futility will be performed at Week 24 when the last randomized subject in Stage 1 completes the Week 24 visit. This analysis will be conducted to evaluate whether the BMS-955176 arm shows significantly worse antiviral efficacy than the TDF arm. The proportion of subjects with HIV-1 RNA < 40 c/mL at Week 24 will be evaluated using the FDA snapshot algorithm. The comparison of the BMS-955176 arm to the TDF arm will be made with one-sided Fisher's exact test, conducted at the 0.01 probability level.

An analysis of virologic futility will also be performed at Week 24 when the last randomized subject in Stage 2 completes the Week 24 visit. This analysis will be conducted to evaluate

whether the BMS-955176 arms show significantly worse antiviral efficacy than the TDF arm in Stage 2. The proportion of subjects with HIV-1 RNA < 40c/mL at Week 24 will be evaluated using the snapshot algorithm. The comparisons of Arms 3 and 4 (BMS-955176) to Arm 5 (TDF) will each be made with a one-sided, Fisher’s exact test, conducted at the 0.01 probability level.

7.6 Safety

Safety endpoints include the frequency of adverse events (AEs), serious adverse events (SAEs), non-serious adverse events, CDC Class C AIDS events, adverse events leading to discontinuations, deaths and other significant adverse events as reported on case report forms. Other safety endpoints include laboratory abnormalities, changes in laboratory parameters, changes in vital signs and physical measurements, and ECGs. Safety endpoints will not be evaluated through a specific analysis week. All safety data available in the database at the time of the lock will be included.

Safety summaries are provided for treated subjects by as-treated treatment arm, unless otherwise specified.

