Based upon the Week 24 analysis of Arms 1 and 2, combined with the Week 24 analysis of all arms in the parallel AI468038 study, a continuation dose of BMS-955176 for Arm 1 will be selected for subjects in Arm 1. Subjects in the BMS-955176 treatment arm 1 may subsequently be transitioned to a selected continuation dose of BMS-955176. Subjects in the Arm containing TDF (i.e., Arm 2) will continue with the TDF treatment regimen. The assigned backbone will remain unaltered. The Week 24 efficacy, safety and pharmacokinetic analyses from Stage 1 and study AI468038 will also trigger the start of Stage 2. If the continuation dose cannot be clearly identified using the Week 24 data, the study will continue in original fashion until an analysis of the Week 48 data can be performed and the continuation dose is selected. If a continuation dose cannot be selected based upon the Week 24 data, this does not preclude the ability to start recruitment of Stage 2.

After the continuation dose is selected and once all of the logistics have been completed globally, the transition of the subjects in Arm 1 to the continuation dose will occur. It is anticipated that this transition will occur on or after all subjects have reached Week 48.

Selection of Continuation Dose and Switch for Stage 2

Once all subjects in Stage 2 have reached Week 24, BMS will conduct an interim analysis of efficacy, safety, resistance and pharmacokinetics. An analysis of virologic futility will also occur at Week 24. If a BMS-955176 dose arm meets criteria for virologic futility at Week 24, subjects in said arm will begin dosing with the next highest available remaining dose of BMS-955176.

The totality of data from AI468038 and AI468048 (Stage 1 and 2) will be used to select a continuation dose of BMS-955176 for Arms 3 and 4. Subjects in the BMS-955176 treatment arms 3 and 4 will subsequently be transitioned to the selected continuation dose of BMS-955176. It is anticipated that this transition may occur on or after all subjects in Stage 2 have reached Week 48. The assigned backbone will not change. Subjects in the TDF-containing arm (i.e., Arm 5) will continue with their assigned treatment regimen.

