6.2 Treatment Regimens

The treatment regimens are defined as follows:

- As-randomized refers to the treatment regimen assigned at randomization. Accrual, disposition, demographic and baseline characteristics, protocol deviations and efficacy results will be presented as-randomized.
- As-treated refers to the actual treatment regimen received. Subjects who receive an incorrect study therapy for the entire period of treatment are grouped according to the first incorrect study regimen received. Otherwise, subjects are grouped according to their randomized treatment regimen. Subjects who never receive study therapy, have their as-treated treatment regimen coded as “missing”. Results for exposure, concomitant medication, resistance, safety and PK parameters, and outcomes research scales will be presented as-treated.

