7.1 General Methods

This is an estimation study. Formal comparisons of treatment arms will not be performed except for the virologic futility analyses performed at Week 24 of Stage 1 and Stage 2 (see [Section 7.5.4](#)).

Presentations will present treatment arms as the original treatment arms, before the potential movement to the continuation BMS-955176 dose. Data from Arms 2 and 5 will not be pooled unless otherwise specified. Separate outputs will be created for each stage unless otherwise specified.

Categorical variables will be tabulated with counts and percentages.

Continuous variables will be summarized with univariate statistics.

Subjects must have a baseline measurement and at least one on-treatment measurement to be evaluable for change from baseline analyses. All data will be displayed for statistics that do not depend on a baseline measurement.

Laboratory parameters will be summarized using SI and US values and units.

Statistical analyses are carried out in SAS version 9.1.3 (Statistical Analysis System, SAS Institute, North Caroline, USA) or higher, unless otherwise indicated.

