7.6.1 Overall Adverse Events

Adverse events will be classified by primary System Organ Class (SOC) and Preferred Term (PT) according to the latest version of the Medical Dictionary for Regulatory Activities (MedDRA) in production at BMS at the time of database lock.

AEs and SAEs with an onset on or after the start of study therapy through 30 days after the last dose of study therapy will be considered as occurring during study therapy. These will be summarized and presented by SOC and PT both in descending order of frequency over all treatment arms, unless otherwise specified.

Table 7.6.1-1: Adverse Event Summaries

Endpoint	During Study Therapy	During Study Therapy, after Switch to Continuation Dose
SAEs	X	X
SAEs leading to death ^a	X	
SAEs related to study therapy and leading to death ^a	X	
Non-SAEs ≥ 5% ^a	X	
AEs leading to discontinuation of study therapy	X	X
AEs - All Grades	X	
AEs - Grade 2 to 4	X	
AEs- Grade 3 to 4	X	

Table 7.6.1-1: Adverse Event Summaries

Endpoint	During Study Therapy	During Study Therapy, after Switch to Continuation Dose
Related AEs - All Grades	X	
Related AEs - Grade 2 to 4	X	
Related AEs - Grade 3 to 4	X	
CDC Class C AIDS Events	X	
Events of Special Interest	X	
Exposure-adjusted Events $\geq 5\%$	X	
Exposure-adjusted SAEs ^a	X	
Exposure-adjusted SAEs related to study therapy ^a	X	
Exposure-adjusted non-SAEs $\geq 5\%$ ^a	X	

a ClinicalTrials.gov or EudraCT reporting requirement

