7.6.4 Serious Adverse Events Emerging After Switch to Continuation Therapy

For subjects who switched to a continuation dose after Week 24, rather than starting on a continuation dose at the time of randomization, SAEs with an onset after the start date of continuation therapy through 30 days after the last dose of study therapy, will be summarized by SOC and PT.

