8.2 Derived Dates

- Start date of any study therapy is the earliest start date of BMS-955176, TDF, ATV, RTV or DTG identified from dosing records with non-missing start date. This date is used to identify treated subjects and to distinguish pre-treatment from any on-study measurements.
- Start date of continuation dosing of study therapy for BMS-955176 is the earliest start date of the continuation dose(s) of BMS-955176 with non-missing daily dose and non-missing start date. This date is used to identify treated subjects receiving the continuation dose(s) of BMS-955176 and to distinguish on-study measurements in the original dosing period from on-study measurements in the continuation dosing period.
- Start date of serum lipid-reducing agents is the earliest start date of any concomitant or post-treatment medication from the therapeutic class ‘serumlipidreducing agent’. This date is used to exclude data in longitudinal lipid analyses during treatment.
- Analysis week date is the start date of study therapy plus the upperbound of the window defining the analysis week minus 1 day (see [Section 8.1](#)). This date is used to include data through the analysis week.

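### Apart from two supplementary tables, no AE, worst-grade laboratory or longest-interval ECG summary in SAP version 2.0 separates data before and after the move to the continuation dose

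*SAP*

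**What the plan says.** **Column.** Section 7.1: "Presentations will present treatment arms as the original treatment arms, before the potential movement to the continuation BMS-955176 dose". Section 7.6: "Safety summaries are provided for treated subjects by as-treated treatment arm, unless otherwise specified". The as-treated rule in Section 6.2 reassigns only subjects who received an incorrect therapy for their whole treatment period. For everyone else: "Otherwise, subjects are grouped according to their randomized treatment regimen". A planned switch therefore leaves the subject in the randomised column.

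**Data.** Section 7.6: "All safety data available in the database at the time of the lock will be included". The AE window in Section 7.6.1 covers "AEs and SAEs with an onset on or after the start of study therapy through 30 days after the last dose of study therapy", so it runs straight through a switch. Worst laboratory grade (7.6.13.1) and longest ECG interval or largest ECG change (7.6.14) are taken over the whole treatment period.

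**Switch.** Section 2.1 says Arm 1 may, and Arms 3 and 4 will, move to a selected continuation dose. For Stage 2: "It is anticipated that this transition may occur on or after all subjects in Stage 2 have reached Week 48". Stage 1 has the same expectation.

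**What is separated.** Section 7.6.4 provides that "SAEs with an onset after the start date of continuation therapy through 30 days after the last dose of study therapy, will be summarized". Section 7.6.7 does the same for AEs leading to discontinuation, and Section 7.4.1 summarises exposure after the switch. Section 8.2 derives a continuation start date, used among other things "to distinguish on-study measurements in the original dosing period from on-study measurements in the continuation dosing period".

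**The concern.** Arms 3 and 4 differ only in the BMS-955176 dose (120 and 180 mg). If either dose is selected, one of these arms spends its later weeks on the other arm's dose while its data stay under the original label. If some other dose is selected, both arms are mixed. A difference between doses in Grade 3-4 AEs, related Grade 2-4 AEs, gastrointestinal events or exposure-adjusted rates would then be pulled towards no difference in the Week 96 tables. The integrated tables of Section 7.8, which have separate columns for Arms 1, 3 and 4, would carry the same mixing.

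Maxima are particularly exposed: a single post-switch value can set a subject's worst laboratory grade or longest QTcF under a dose no longer being taken. The plan recognises the two dosing periods and defines the date that divides them, but applies it to few safety outputs.

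**Working it through.** The plan states no figure on this point, so there is none to reproduce. The check has two parts.

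**1. What is split.** Table 7.6.1-1 has 17 endpoints. Two are marked in the post-switch column: SAEs and AEs leading to discontinuation. That is 2/17 = 12%, leaving 15. Among the 15 are all-grade, Grade 2-4 and Grade 3-4 AEs, their related counterparts, events of special interest and the four exposure-adjusted rows. Sections 7.6.13 to 7.6.15 (laboratory, ECG, vital signs) contain no split.

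The two post-switch tables are additions: the same events remain in the during-therapy tables. Pre-switch counts cannot be recovered by subtraction, because Section 8.6 counts a subject once per preferred term in an analysis period. Someone with the same event in both periods appears once in the main table and once in the post-switch table.

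**2. Scale, under stated assumptions.** Inputs from the SAP: 96 weeks of treatment, and a switch no earlier than the last subject's Week 48. Assumed: uniform accrual over *a* weeks, everyone switching at that moment, everyone completing Week 96, and constant rates of 20 and 40 events per 100 person-years at the two doses (true ratio 2.0).

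Share of treatment time on the continuation dose: f = (48 − a/2)/96.

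Rate shown for the switched arm:
- if the lower-rate arm switches: 20(1 − f) + 40f, compared with 40 in the other arm
- if the higher-rate arm switches: 40(1 − f) + 20f, compared with 20 in the other arm

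| a (weeks) | f | Lower-rate arm switches: rate shown | Ratio shown | Higher-rate arm switches: rate shown | Ratio shown |
|---|---|---|---|---|---|
| 0 | 0.50 | 30 | 40/30 = 1.33 | 30 | 30/20 = 1.50 |
| 24 | 0.375 | 27.5 | 40/27.5 = 1.45 | 32.5 | 32.5/20 = 1.63 |
| 48 | 0.25 | 25 | 40/25 = 1.60 | 35 | 35/20 = 1.75 |

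The true ratio of 2.0 is shown as 1.33 to 1.75. Dilution occurs in both directions. A later switch, for instance because global logistics take time (Section 2.1), reduces f and the dilution.

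**The case against.** Much can be said for the plan.

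- **The named safety endpoints are covered.** SAEs and AEs leading to discontinuation are the AE endpoints of the safety and tolerability objective, and both have post-switch tables. A reader might infer that every AE table mixes doses with no remedy; these tables show otherwise.
- **Earlier locks are nearly clean.** Full safety tables are run at the Stage 2 Week 24 and Week 48 locks. Given the expected switch timing, the first is pre-switch and the second essentially so. Creatinine, lipids and ECG intervals are also summarised by visit, so visits before the switch can be read separately.
- **Events are traceable.** The AE and laboratory listing templates show current treatment.
- **Original-arm columns are a disclosed choice** that preserves the randomised grouping. Cutting the main tables at the switch only for switchers would give arms unequal follow-up. Crude incidence and maxima rise with follow-up, so the truncated arm could look safer.
- **The 2017 appendix supersedes version 2.0.** The study ended before all subjects reached the Week 24 primary endpoint, while the switch was expected only after all subjects in a stage had reached Week 48. The appendix display list has no exposure-adjusted AE tables.

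These points confine the problem to the Week 96 and integrated tables and rule out truncating the main tables. They do not supply a pre-switch summary, or a post-switch summary for the remaining endpoints. Listings are no substitute for either.

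**Conclusion.** The point holds for version 2.0 in this limited form: safety data after the switch stay under the original dose, and outside two supplementary AE tables no AE, worst-grade laboratory or longest-interval ECG summary separates the periods. It affects only subjects whose continuation dose differs from their assigned dose. The range of 1.33 to 1.75 for a true ratio of 2.0 rests on assumed rates, immediate switching and full completion; it illustrates scale and does not estimate the trial's effect.

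A reader might infer that the reported safety results are contaminated. The documents do not support that: they never say that anyone switched, and early termination means few or no switches may have occurred. However, the appendix's safety display list (Section 3.3.1) omits both post-switch AE tables and the post-switch exposure table. Any switch that did take place would have no separate summary at all. The point concerns reporting only and implies nothing about which dose is right.

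**What to change.** 1. Keep the all-data tables by original arm as they are.
2. Using the Section 8.2 date, extend the post-switch column of Table 7.6.1-1 to Grade 3-4 AEs, Grade 2-4 related AEs, gastrointestinal events and exposure-adjusted rates. Add a matching post-switch summary of Grade 3-4 laboratory toxicities.
3. Add supplementary pre-switch summaries of the same endpoints and of longest ECG intervals. Cut person-years at the switch, and footnote that follow-up then differs between arms.
4. In the 2017 appendix, state whether any subject moved to a continuation dose. If none did, one sentence closes the point. If any did, apply the same split to the final displays.

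The cost is SAP wording and extra runs of existing templates; the date variable is already specified. The trade-off is shorter and unequal follow-up in the pre-switch summaries, which is why they should stand beside the all-data tables and not replace them.
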